3.1 Registration – Inclusion Criteria

3.11 Classical Hodgkin Lymphoma determined by local hematopathology review

3.12 One of the following:

- Age \geq 60 years
- Age <60 years but unsuitable for standard chemotherapy because of a cardiac ejection fraction of <50%, a pulmonary diffusion capacity <80%, or a creatinine clearance \geq 30 and <60 mL/min, or refused standard chemotherapy despite efforts to convince them otherwise.

Cockcroft-Gault Equation:

$$\text{Creatinine clearance for males} = \frac{(140 - \text{age})(\text{weight in kg})}{(72)(\text{serum creatinine in mg/dL})}$$

$$\text{Creatinine clearance for females} = \frac{(140 - \text{age})(\text{weight in kg})(0.85)}{(72)(\text{serum creatinine in mg/dL})}$$

- 3.13 Requirement for systemic chemotherapy: all stages except IA (not bulky disease), if involved field is considered Radiotherapy (RT) curative.
- 3.14 Previously untreated with either chemotherapy, radiation therapy or either brentuximab vedotin or nivolumab, or another check point inhibitor.
- 3.15 ECOG Performance Status (PS) 0, 1, or 2 (Appendix II)
- 3.16 The following laboratory values obtained ≤ 7 days prior to registration.
- Absolute neutrophil count (ANC) $\geq 1500/\text{mm}^3$, unless secondary to bone marrow involvement.
 - Leukocytes $\geq 3,000/\text{mm}^3$
 - Platelet count $\geq 100,000/\text{mm}^3$
 - Hemoglobin >9.0 g/dL – unless determined by treating physician to be disease related
 - Total bilirubin ≤ 1.5 x upper limit of normal (ULN)
 - Aspartate transaminase (AST) ≤ 2.5 x ULN
 - Alanine Transaminase (ALT) ≤ 2.5 x ULN
 - Creatinine ≤ 2.0 mg/dL
 - Amylase and/or lipase ≤ 1.5 x ULN
- 3.17 Women of childbearing potential must have a negative serum or urine pregnancy test (minimum sensitivity 25 IU/L or equivalent units of HCG) within 24 hours prior to registration

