3.26 Allergy to Brentuximab Vedotin and/or Nivolumab

3.27 Uncontrolled intercurrent illness including, but not limited to, ongoing or active infection, symptomatic congestive heart failure, unstable angina pectoris, cardiac arrhythmia, or psychiatric illness/social situations that would limit compliance with study requirements.

3.28 Receiving any other investigational agent which would be considered as a treatment for the primary neoplasm.

3.29a Have had prior chemotherapy or radiotherapy for Hodgkin lymphoma

3.29b Have received either of the study drugs

3.29c <60 years who are considered candidates for standard chemotherapy

- 3.29d \geq Grade 2 peripheral neuropathy
- 3.29e Other active malignancy \leq 2 years prior to registration, unless treated with curative intent. EXCEPTIONS: Non-melanotic skin cancer or carcinoma-in-situ of the cervix. NOTE: If there is a history or prior malignancy, they must not be receiving other specific treatment for their cancer.
- 3.29f Active CNS involvement or leptomeningeal metastases involvement.
- 3.29g Known history of pancreatitis.

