4.0 Test Schedule

Tests and procedures	Active Monitoring Phase				
	Baseline <14 days of Registration	Prior to each new cycle ¹⁰ <= 3 days (starting at cycle 2)	Restaging End of Cycle 8 (6-8 Weeks after Day 1 of Cycle 8)	End of Treatment if discontinued early (at PD or PMD, withdrawal, or removal)	Observation (Every 30 days x 90 days, , then every 90 days x 2.5 years, then every 6 months until 5 years from registration) +/-14Days
History and exam	X	X ¹	X	X	X
B Symptoms ⁹	X	X	X	X	X
ECOG PS	X	X	X	X	X
Height (baseline only), Weight	X	X	X	X	X
Adverse event assessment	X	X	X	X	X
Cardiac ejection fraction	X ¹⁴				
ECG	X				
Pulmonary function studies (including oxygen saturation) ¹²	X				
HBV sAg and HCV Ab or HCV RNA	X				
Comprehensive metabolic panel: (ALT, AST, total bilirubin, alkaline phosphatase), BUN or serum urea level, creatinine, Ca, Mg, Na, K, Cl, LDH, Glucose, amylase, lipase, Albumin, bicarbonate	X ⁴	X	X	X	
INR ^{K, 13}		X	X	X	X
TSH (with Free T4 and Free T3)	X ⁴	X ¹¹	X	X	
Hematology: CBC/differential	X ⁴	X	X	X	X
Erythrocyte sedimentation rate	X				
Uric Acid	X				
Pregnancy Test ³	X	X	X	X	X
PET-CT	X ¹⁴	X ²	X	X	
CT scan Chest/Abd/Pelvis					X ⁵
Mandatory Research blood samples (See section 14.0) ^{K, 6}		X ¹⁵	X	X	X ⁸
Mandatory Tissue sample ^{7, K}	X				

(Footnotes on next page)

- 1 If on physical exam there are any palpable lymph nodes present: Tumor (bidimensional)-measurements by physical exam to be done at end of every cycle, prior to next cycle.
- 2 End of cycle 2, prior to Cycle 3 (≤ 5 days)
- 3 For women of childbearing potential only. A serum or urine pregnancy testing is required ≤ 24 hours before registration, then every other cycle. (more frequently if required by local standard). After discontinuation from nivolumab, these should be repeated at approximately 30 days and approximately 70 days [or more frequently if required by local standard].
- 4 Must be obtained ≤ 7 days prior to registration.
- 5 CT scan is every 3 months during the first year of observation, then as clinically indicated.
- 6 Must be drawn on Day 1 of each cycle before treatment Cycles 1-8, at restaging 6-8 weeks post Cycle 8 Day 1, end of treatment if discontinued early (PD or PMD, withdrawal or removal), and at time of PD or PMD.
- 7 To be submitted within ≤ 14 days following Registration; see 17.0 Pathology Considerations/Tissue Biospecimens
- 8 Only at time of PD or PMD

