***starting dose level**

7.12 Definition of Dose Limiting Toxicity (DLT)

For this protocol, dose-limiting toxicity (DLT) will be defined as an adverse event occurring during the first cycle of treatment that is possibly, probably, or definitely related to study treatment and that meets one of the following:

- Any \geq Grade 4 non-hematological organ toxicity (except for Grade 4 nivolumab related diarrhea, pneumonitis, LFT elevations, that improve within 7 days)
- Any \geq Grade 4 hematological toxicity (excluding asymptomatic Grade 4 elevations in amylase or lipase)

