→ → Use the NCI Common Terminology Criteria for Adverse Events (CTCAE) version 4.0* unless otherwise specified ← ←			
CTCAE System/Organ/Class (SOC)	ADVERSE EVENT	AGENT	ACTION**
Investigations	Creatinine Increased	Nivolumab	
Patients will be monitored for elevated serum creatinine prior to and periodically during treatment. Administer corticosteroids at a dose of 1 to 2 mg/kg/day prednisone equivalents followed by corticosteroid taper for life-threatening (Grade 4) serum creatinine elevation and permanently Discontinue nivolumab; continue BV at the same dose level.
 
For severe (Grade 3) or moderate (Grade 2) serum creatinine elevation, withhold nivolumab and administer corticosteroids at a dose of 0.5 to 1 mg/kg/day prednisone equivalents followed by corticosteroid taper; if worsening or no improvement occurs, increase dose of corticosteroids to 1 to 2 mg/kg/day prednisone equivalents and permanently Discontinue nivolumab; continue BV at the same dose level.

Investigations	Neutrophil (ANC) count decreased	Brentuximab Vedotin (BV) and Nivolumab	
≥Grade 3; hold both BV and nivolumab until resolved to grade 1 (or baseline). At this point myeloid growth factors can be used at investigator's discretion.
 
If not resolved to ≤Grade 1 or better within 28 days, discontinue nivolumab and BV. Patient should go to event monitoring per Section 18.

→ → Use the NCI Common Terminology Criteria for Adverse Events (CTCAE) version 4.0* unless otherwise specified ← ←			
CTCAE System/Organ/Class (SOC)	ADVERSE EVENT	AGENT	ACTION**
	Amylase and/or lipase increase	Brentuximab Vedotin (BV) and Nivolumab	Grade ≥ 3: Hold BV and nivolumab until resolved to ≤Grade 2, then resume at same dose, per protocol. If there is clinical or radiographic evidence of pancreatitis, refer to pancreatitis AE actions (below).

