Renal Impairment: No clinically important differences in the clearance of nivolumab were found between subjects with mild or moderate renal impairment and subjects with normal renal function. Data from subjects with severe renal impairment are too limited to draw conclusions on this population.
Hepatic Impairment: No clinically important differences in the clearance of nivolumab were found between subjects with mild hepatic impairment and normal hepatic function. Nivolumab has not been studied in subjects with moderate (total bilirubin > 1.5 to 3 times ULN and any AST) or severe hepatic impairment (total bilirubin > 3 times ULN and any AST).

- 15.26 **Potential Drug Interactions:** Nivolumab is an IgG4 monoclonal antibody, which is eliminated by mechanisms similar to that of other antibodies, namely by non-specific catabolism (mainly by enzymes in the reticuloendothelial system). These enzymes are not known to be inhibited or induced by drugs, and therefore it is unlikely that other drugs will have an impact on the PK of nivolumab.
- 15.27 **Known potential toxicities:** (from package insert): Consult the package insert for the most current and complete information.

Very common known potential toxicities (>10%):

Cardiovascular: Edema ($\leq 13\%$), peripheral edema ($\leq 13\%$), hypertension (11%)

Central nervous system: Fatigue ($\leq 59\%$), malaise ($\leq 46\%$), headache (16% to 23%), dizziness ($\leq 14\%$), peripheral neuropathy ($\leq 14\%$; grade 3: $< 1\%$)

Dermatologic: Skin rash (1% to 40%; immune-mediated: 9% to 16%), pruritus (10% to 28%), vitiligo ($\leq 11\%$)

Endocrine & metabolic: Hyperglycemia (19% to 46%), hyponatremia (19% to 41%), increased serum triglycerides (32%), hyperkalemia (11% to 30%), increased thyroid stimulating hormone level ($\geq 10\%$ to 26%), hypocalcemia (10% to 26%), increased serum cholesterol (21%), hypercalcemia (2% to 19%), thyroiditis ($\leq 12\%$ to 18%; including immune-mediated events), hypomagnesemia (14% to 17%), hypokalemia (14% to 16%), thyroid dysfunction (15%), hypothyroidism ($\leq 12\%$; including immune-mediated events)

Gastrointestinal: Diarrhea (1% to 43%), nausea (20% to 34%), abdominal pain (13% to 34%), increased serum lipase (20% to 33%), decreased appetite (14% to 28%), vomiting (12% to 28%), constipation (10% to 23%), increased serum amylase (13% to 19%)

Genitourinary: Urinary tract infection (2% to 17%)

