and quantitatively summarized and explored. Standard paired comparisons methodologies (paired t-tests, Wilcoxon signed rank tests and Fisher's exact tests for interval, ordinal and nominal level data, respectively) will be used to assess changes in these variables before and after therapy. In addition, baseline values and changes over time in each measure will be explored in relation to clinical outcome to explore any differences between responders and non-responders and by depth of response (CMR vs. PMR) to identify potential biomarkers.

- 16.4 Early Safety Analysis: An early safety analysis will be performed after the first 6 patients have been accrued to the study at dose level 1 and observed for one cycle. If 2 or more of the first 6 patients experience a DLT as defined in Section 7.12, then the starting dose level will be adjusted and additional cohorts may be evaluated at dose levels -1 and -2 as described below. Accrual will be halted while evaluating each cohort in the early safety analysis.
- 16.41 Dose level +1: Six evaluable patients will be accrued onto dose level +1 and observed until they complete one cycle treatment. If 0 or 1 out of 6 patients experience a DLT, accrual will continue in the phase II portion at dose level 1. If 2 or more patients experience a DLT on dose level +1, the toxicity level for dose level +1 will be considered unacceptable and six additional patients will be treated on dose level -1.
- 16.42 Dose de-escalation to Dose level -1: If dose level +1 has an unacceptable level of toxicity, six evaluable patients will be accrued onto dose level -1. If 0 or 1 out of 6 patients experience a DLT on dose level -1, accrual will continue in the phase II portion at dose level -1. If 2 or more patients experience a DLT, the toxicity level for dose level -1 will be considered unacceptable and six additional patients will be treated on dose level -2.
- 16.43 Dose escalation to Dose level -2: If dose level -1 has an unacceptable level of toxicity, six evaluable patients will be accrued onto dose level -2. If 0 or 1 out of 6 patients experience a DLT on dose level -2, accrual will continue in the phase II portion at dose level -2. If 2 or more patients experience a DLT, the toxicity level for dose level -2 will be considered unacceptable and accrual to the study will be temporarily closed, evaluated and potentially amended.
- 16.5 Data & Safety Monitoring:

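### Section 7.12 attaches the amylase/lipase exclusion to the hematological DLT bullet, where it excludes nothing; it belongs on the non-hematological bullet

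*Combined protocol and SAP*

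**What the plan says.** Section 7.12 counts an event as a DLT if it occurs in cycle 1, is at least possibly related to treatment, and falls under one of two bullets.

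- **Non-hematological bullet:** organ toxicity of grade 4 or higher, "except for Grade 4 nivolumab related diarrhea, pneumonitis, LFT elevations, that improve within 7 days". Amylase and lipase are not mentioned.
- **Hematological bullet:** toxicity of grade 4 or higher, "excluding asymptomatic Grade 4 elevations in amylase or lipase".

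Section 16.4 applies this definition without restating it: "If 2 or more of the first 6 patients experience a DLT as defined in Section 7.12", the starting dose level is adjusted. Under Section 7.11 the next level down, -1, keeps brentuximab vedotin at 1.8 mg/kg and omits nivolumab.

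Section 15.27 places "increased serum lipase (20% to 33"%) in the gastrointestinal group of nivolumab toxicities, with amylase. Its hematologic group contains only anemia, lymphocytopenia, leukopenia, thrombocytopenia and neutropenia. For a grade 3 or higher amylase or lipase increase, Section 8.2 holds both drugs until grade 2 or better and then resumes them at the same dose. It treats pancreatitis separately: "If there is clinical or radiographic evidence of pancreatitis, refer to pancreatitis AE actions (below").

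**The concern.** An exclusion can only take out what its category contains. Pancreatic enzyme rises are not in the hematological category, so the clause does nothing where it stands. The bullet that could capture them has no such exclusion. The definition as written can therefore count an event that its authors evidently meant to leave out.

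Section 7.12 is the only DLT definition, and the six-patient rule in Section 16.4 depends on it. One miscounted laboratory event would supply half of the trigger that removes nivolumab, and phase II could then proceed without the combination that the trial was set up to study. This is a drafting error; no design decision is in question.

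**Working it through.** **Text check**

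1. *Does the hematological bullet contain amylase or lipase rises?* No. Section 15.27 puts them under gastrointestinal effects, and its hematologic list is cytopenias only.
2. *Could hematological mean any abnormal blood test?* No. Liver function tests are also blood tests, and Section 7.12 handles them on the non-hematological bullet.
3. *Does the non-hematological bullet reach enzyme rises?* Its wording is limited to organ toxicity, which leaves some doubt. But it has to except LFT elevations, which implies that laboratory enzyme rises are in scope unless excepted. Amylase and lipase are not excepted.
4. *Is it corrected elsewhere?* No. Section 16.4 only points back to Section 7.12.
5. *Is the intent clear?* Yes, from the clause itself and from the hold-and-resume rule in Section 8.2.

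**Size of the effect**

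The plan gives no figure to reproduce on this point. The inputs are:

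- Rule: 2 or more DLTs in 6 patients (Section 16.4).
- *o*, the per-patient probability of any other DLT: assumed 5% or 10%.
- *e*, the per-patient probability of a related, asymptomatic grade 4 amylase or lipase rise in cycle 1: not given in the documents; assumed 1% or 2%, with 5% as an upper sensitivity case.
- The two are taken as independent.

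As written, p = 1 − (1 − o)(1 − e). With the clause on the right bullet, p = o. The chance of crossing the rule is P = 1 − (1 − p)^6 − 6p(1 − p)^5.

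For example, with o = 0.10 and the clause moved: 1 − 0.5314 − 0.3543 = 0.1143. With e = 0.01 as written: p = 1 − 0.90 × 0.99 = 0.109 and P = 0.1324.

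| e | p (o = 0.10) | P (o = 0.10) | p (o = 0.05) | P (o = 0.05) |
|---|---|---|---|---|
| 0 (clause moved) | 0.100 | 0.1143 | 0.0500 | 0.0328 |
| 0.01 | 0.109 | 0.1324 | 0.0595 | 0.0452 |
| 0.02 | 0.118 | 0.1513 | 0.0690 | 0.0593 |
| 0.05 (upper case) | 0.145 | 0.2118 | 0.0975 | 0.1094 |

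At o = 0.10 the increase is 0.1324 − 0.1143 = 0.018 for e = 1% and 0.1513 − 0.1143 = 0.037 for e = 2%. Enzyme rises alone (o = 0) would cross the rule with probability 0.0015 at 1% and 0.0057 at 2%.

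**Which rates are plausible**

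Several points in the protocol favour the low end:

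- Entry requires "Amylase and/or lipase ≤ 1.5 x ULN" (Section 3.16), and "Known history of pancreatitis" is an exclusion (Section 3.29g).
- Section 1.1 reports no grade 4 or 5 events in 23 nivolumab-treated Hodgkin patients, although 13% had a lipase increase. This does not rule out 5%: zero of 23 has a one-sided 95% upper bound of 1 − 0.05^(1/23) ≈ 0.12.
- The panel with "Glucose, amylase, lipase, Albumin, bicarbonate" (Section 4.0) has only one scheduled post-dose draw that covers cycle 1, the one before cycle 2, so short-lived rises may be missed. If half were detected, the figures at o = 0.10 become 0.1232 (e = 1%) and 0.1324 (e = 2%).

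**The case against.** The strongest reply accepts the misplacement and denies that it has consequences.

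- **Intent is obvious.** The only sensible purpose of the clause is to stop these events counting. Section 7.1 provides weekly investigator calls and requires prompt contact about any DLT, so a case would be discussed. This stands as a reason to expect the intended reading. It does not make the text right: a DLT definition should give the same count at every site without anyone inferring intent.
- **An isolated enzyme rise may not be organ toxicity.** Section 8.2 stops both drugs for grade 4 transaminase or bilirubin rises but resumes both at the same dose after an amylase or lipase rise, so the LFT analogy is imperfect. On this reading the event meets neither bullet and nothing changes in practice. The ambiguity is real. Even so, the clause has no effect where it stands, and the non-hematological bullet remains open to the other reading.
- **The toxicity list in Section 15.27 comes from the package insert and does not govern DLT grading.** Section 8.2 groups blood counts and transaminases together under Investigations. That is correct, but nothing in either scheme makes lipase a hematological toxicity.
- **The rates are assumed.** They are, and the 5% case should not be taken as an expectation.
- **A second parenthesis could seem to inherit the 7-day condition of the first.** This is a fair drafting point, which the fix has to meet.

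**Conclusion.** The point holds as a minor wording error. That the clause is misplaced is certain from the text. That it would change a DLT count is less certain, because it depends on how the organ-toxicity wording is read and on whether such an event occurs in cycle 1.

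If it is read literally, and with other DLTs at an assumed 5% to 10%, the chance of dropping nivolumab after the first six patients rises by about 1 to 4 percentage points for assumed enzyme rates of 1% to 2%. These figures rest on the assumed rates and on independence. The effect is confined to the six-patient safety cohorts and the dose taken into phase II. The primary endpoint, the 56-patient sample size and the 17/25 and 40/56 decision rules are untouched.

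**What to change.** In Section 7.12, delete "excluding asymptomatic Grade 4 elevations in amylase or lipase" from the hematological bullet and place it on the non-hematological bullet. Keep it as a separate parenthesis after the existing one, so that the 7-day improvement condition is not read as applying to amylase and lipase. Section 16.4 needs no edit, because it refers to Section 7.12.

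The cost is moving one parenthesis. Sample size, data collection and decision thresholds stay as they are.

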7.2 Treatment Schedule - Use actual weight

7.21 Pretreatment medication

Agent	Dose Level	Route	Day	Cycle Length
Acetaminophen ¹	650 mg	PO	Day 1	Cycles 1-7 (21 days) Cycle 8 (6-8 weeks)
Diphenhydramine ¹	25-50 mg	IV infused or PO at least 30 minutes prior to brentuximab Vedotin and Nivolumab infusions	Day 1	Cycles 1-7 (21 days) Cycle 8 (6-8 weeks)
Hydrocortisone ¹ (or other steroid equivalent)	100 mg	IV infused at least 30 minutes prior to brentuximab Vedotin and Nivolumab infusions	Day 1	Cycles 1-7 (21 days) Cycle 8 (6-8 weeks)

1. If Brentuximab Vedotin is omitted there are no premedications to be given with just Nivolumab.

7.22 Treatment Schedule

Agent	Dose Level	Route	Day	Cycle Length
Brentuximab vedotin	1.8 mg/kg (cap at 180 mg) in 100 to 250 mL NS to final concentration 0.4 mg/mL to 1.8 mg/mL	IV infused over 30 minutes, before nivolumab	Day 1	Cycles 1-7 (21 days) Cycle 8 (6-8 weeks)
Nivolumab	3 mg/kg in 100 cc NS	IV infused over 60 minutes. 1 hour after completion of Brentuximab vedotin	Day 1	

7.222 The dosing calculations should be based on the actual body weight at baseline. If the subject's weight on the day of dosing differs by > 10% from the weight used to calculate the original dose, the dose must be recalculated. All doses should be rounded to the nearest milligram. Subjects should be carefully monitored for infusion reactions during nivolumab administration. If an acute infusion reaction is noted, subjects should be managed according to Protocol Section 9. Doses of nivolumab may be interrupted, delayed, or discontinued depending on how well the subject tolerates the treatment. Nivolumab Injection, 100 mg/10 mL (10 mg/mL) and 40 mg/mL (10 mg/mL) Nivolumab injection is to be administered as an IV infusion through a 0.2-micron to 1.2-micron pore size, low-protein binding polyethersulfone membrane in-line filter at the protocol-specified doses. It is not to be administered as an IV push or bolus injection. Nivolumab injection can be infused undiluted (10 mg/mL) or diluted with 0.9% Sodium Chloride Injection, USP or 5% Dextrose Injection, USP to protein concentrations as low as 1 mg/mL. Care must be taken to assure sterility of the prepared solution as the product does not contain any antimicrobial preservative or bacteriostatic agent.

7.3 For this protocol, the patient must return to the consenting ACCRU institution for evaluation at least every 21 days during treatment (with the exception of Cycle 8). After therapy completion, the patient must return to the institution, every 30 days x 90 days, then every 60 days x 180 days, then every 90 days x 2 years, then every 6 months until 5 years post registration, during observation (Active Monitoring Phase) until the patient goes to event monitoring per Section 13.0.

7.4 Patients will be treated for a planned maximum of 8 cycles.

7.5 A PET-CT scan will be performed within 5 days prior to starting cycle 3. Patients who

are in CMR or PMR continue treatment for a total of 8 cycles as tolerated. Those with NMR or PMD at the first interim PET-CT (within 5 days prior to starting cycle 3), or who experience PD or PMD any time thereafter go off treatment to event monitoring and are treated as per their primary hematologist/oncologist.

- 7.6 For this protocol, the patient must return to the consenting institution for evaluation at least every 21 days (+/- 3 days) during protocol treatment. Protocol treatment may not be administered by a local medical doctor (LMD).

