15.2 Nivolumab (Opdivo®, BMS-936558)

- 15.21 **Background:** Nivolumab is a human immunoglobulin G4 (IgG4) monoclonal antibody that selectively inhibits programmed cell death-1 (PD-1) activity by binding to the PD-1 receptor to block the ligands PD-L1 and PD-L2 from binding. The negative PD-1 receptor signaling that regulates T-cell activation and proliferation is therefore disrupted. This releases PD-1 pathway-mediated inhibition of the immune response, including the antitumor immune response.
- 15.22 **Formulation:** Available for injection 10mg/ml (4mL, 10mL, 24mL) in a single-use vial [contains in sodium citrate, sodium chloride, mannitol, diethylenetriaminepentacetic acid (pentetic acid), polysorbate 80, and water for injection]
- 15.23 **Preparation and storage:** When the dose is based on patient weight (ie, mg/kg), nivolumab injection can be infused undiluted (10 mg/mL) or diluted with 0.9% Sodium Chloride Injection, USP or 5% Dextrose Injection, USP to concentrations as low as 0.35 mg/mL. When the dose is fixed (eg, 240 mg, 360 mg, or 480 mg flat dose), nivolumab injection can be infused undiluted or diluted so as not to exceed a total infusion volume of 160 mL. For patients weighing less than 40 kilograms (kg), the total volume of infusion must not exceed 4 mL per kg of patient weight. Mix diluted solution by gentle inversion. Do not shake. Discard partially used vials or empty vials. Store at room temperature for no more than -8 hours (includes time of administration) or under refrigeration at 2°C to 8°C (36°F-46°F) for no more than 24 hours from the time of infusion preparation. Protect from light and freezing. If stored in a glass front refrigerator, vials should be stored in the carton. Recommended safety measures for preparation and handling of nivolumab include laboratory coats and gloves. For additional details on prepared drug storage and use time of nivolumab under room temperature/light and refrigeration, please refer to the BMS-936558 (nivolumab) Investigator Brochure section for “Recommended Storage and Use Conditions”
- 15.24 **Administration:** Administer over 30 minutes through a line with a sterile, nonpyrogenic, low protein binding 0.2 to 1.2 micrometer in-line filter. It cannot be administered as an IV push or bolus injection. Do not administer other medications through the same IV line. Flush IV line at the end of the infusion.
- 15.25 **Pharmacokinetic information:**
Distribution: Vd: 8 L
Half-life elimination: ~27days

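### Nivolumab infusion time is 60 minutes in Section 7.22 but 30 minutes in Section 15.24, with nothing to say which governs

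*Combined protocol and SAP*

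**What the plan says.** All of the text at issue is in the combined protocol and SAP.

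- **Infusion time.** The Section 7.22 table has nivolumab "IV infused over 60 minutes. 1 hour after completion of Brentuximab vedotin". Section 15.24 says "Administer over 30 minutes through a line with a sterile, nonpyrogenic, low protein binding 0.2 to 1.2 micrometer in-line filter". Neither gives a range, and neither refers to the other.
- **Minimum dilution.** Section 7.222 permits dilution "to protein concentrations as low as 1 mg/mL". Section 15.23, for weight-based doses such as the one used here, permits it "to concentrations as low as 0.35 mg/mL".
- **Vial strength.** Section 7.222 lists "100 mg/10 mL (10 mg/mL) and 40 mg/mL (10 mg/mL) Nivolumab injection". Section 15.22 has "Available for injection 10mg/ml (4mL, 10mL, 24mL) in a single-use vial".

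Section 7.22 also fixes the preparation at 3 mg/kg in 100 mL of saline on Day 1. Section 7.4 plans at most 8 cycles.

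**The concern.** The infusion times exclude each other. A nurse working from the treatment schedule and one working from the drug information section would give the same dose over different times, and each would be following the protocol as written.

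Three features make uniform administration worth securing:

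- Section 7.1 says the combination has not been studied to date. The first 6 patients decide whether the starting dose stands, and 2 or more dose-limiting toxicities (DLTs) lead to an adjustment (Section 16.4).
- Section 7.222 requires careful monitoring for infusion reactions during nivolumab. Section 15.27 lists infusion-related reactions at up to 14% for nivolumab, and Section 1.226 gives about 10% for brentuximab vedotin in its phase 2 studies.
- Safety and tolerability are a secondary goal (Section 2.22), and each participating site orders its own drug (Section 15.281). If sites read the protocol differently, the infusion-reaction data would pool two methods of administration, with nothing in the plan to separate them.

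**Working it through.** **Inputs.** Infusion time 60 min (7.22) and 30 min (15.24). Dose 3 mg/kg in 100 mL (7.22). Dilution floor 1 mg/mL (7.222) and 0.35 mg/mL (15.23). Vial descriptions as quoted (7.222, 15.22). For illustration, a weight of 80 kg, which Section 1.33 gives as the approximate median in nivolumab trials.

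**1. Infusion time.** The ratio is 60/30 = 2.0. The mean rate is dose divided by time. At 80 kg the dose is 3 × 80 = 240 mg, so the rate is 240/60 = 4 mg/min under 7.22 and 240/30 = 8 mg/min under 15.24. The two-fold ratio does not depend on weight. No infusion time satisfies both sections.

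**2. Minimum dilution.** The floors differ by 1/0.35 = 2.86. Both sentences are permissive, so any concentration from 1 mg/mL up to the undiluted 10 mg/mL satisfies both. To see whether the prescribed bag does so, let *w* be weight in kg and take two readings of the 100 mL:

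- final volume 100 mL: concentration = 3*w*/100
- drug at 10 mg/mL added to 100 mL: concentration = 3*w*/(100 + 0.3*w*)

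| Weight | Final volume 100 mL | Added to 100 mL |
|---|---|---|
| 50 kg | 150/100 = 1.50 mg/mL | 150/115 = 1.30 mg/mL |
| 80 kg | 240/100 = 2.40 mg/mL | 240/124 = 1.94 mg/mL |
| 100 kg | 300/100 = 3.00 mg/mL | 300/130 = 2.31 mg/mL |

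The concentration reaches 1 mg/mL at *w* = 100/3 = 33.3 kg on the first reading and *w* = 100/2.7 = 37.0 kg on the second. Only below those weights does the prescribed bag fall under the higher floor.

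**3. Vial strength.** For the first presentation in 7.222, 100 mg/10 mL = 10 mg/mL, which agrees with its bracket. For the second, 40 mg in 1 mL is 40 mg/mL, which does not agree with its bracketed 10 mg/mL; the ratio is 40/10 = 4. Under 15.22, the 4 mL vial at 10 mg/mL holds 4 × 10 = 40 mg. The number 40 therefore fits a vial content, but not the unit printed beside it. Section 7.222 also omits the 24 mL vial listed in 15.22.

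**4. Link to the design.** The decision rules (at least 18 successes in 25, then at least 41 in 56), the null and target proportions of 65% and 80%, and the 0.10 significance level do not use infusion time, dilution or vial strength. None of these figures changes.

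**The case against.** The case against making much of this has four parts.

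**The two sections differ in kind.** Section 7 is the trial's own treatment schedule. Section 15.2 carries general product text, including flat doses that this trial does not use, toxicities taken from the package insert, and remarks on combination with ipilimumab. Sites might well default to Section 7, and the weekly investigator call in Section 7.1 could bring differences to light. This lowers the chance of divergence and is why one should say that sites *could* differ, not that they *would*. It does not settle the conflict. Section 15.24 is also an instruction to those giving the drug, and the documents contain no rule of precedence.

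**Dilution.** A reader might infer that sites cannot comply with both sections on dilution as well. They can, as the working shows. The two statements should agree, but the practical effect is close to nil.

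**Vial strength.** A reader might infer a four-fold dosing hazard. For 210 mg (3 mg/kg at an assumed 70 kg), 10 mg/mL gives 210/10 = 21 mL and 40 mg/mL gives 210/40 = 5.25 mL. To reach the smaller volume, a pharmacist would have to disregard the adjacent bracket, the undiluted strength of 10 mg/mL later in the same paragraph, and Section 15.22. No other text describes a 40 mg/mL product. This is a remote worst case from a probable misprint, and a character lost when the PDF was read cannot be excluded.

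**Consequences.** A reader might also infer that one infusion time is unsafe, or that DLT counts or the response rate would be distorted. The documents support neither. The DLT definition in Section 7.12 counts only related Grade 4 or higher events in cycle 1, and nothing links infusion time to those events or to metabolic response. The dose, the treatment day and the one-hour gap after brentuximab vedotin are not in conflict between the two sections.

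What remains is the infusion time itself, to which the objection has no answer beyond likelihood.

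**Conclusion.** The infusion-time instructions are wrong as written. They differ two-fold, they exclude each other, and nothing says which applies. This is an internal inconsistency in operative text, not a questionable design choice, and it should be corrected. The conclusion rests on the current wording of Sections 7.22 and 15.24 and on the absence of any precedence statement. It needs no assumption about weight, and it takes no position on which time is right.

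The vial description and the two dilution floors are minor items for the same correction. The inability to comply with both sections applies to infusion time only. No effect on DLT counts, the primary endpoint, sample size, significance level or power is shown or claimed.

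**What to change.** - The investigators and drug supplier should reconcile Sections 7.22 and 15.24, state the nivolumab infusion time in one place, and have the other section refer to it. Which value applies is theirs to decide.
- In the same amendment, check and correct the second vial description in Section 7.222 against Section 15.22 and the supplied product.
- Align the minimum-dilution statements in Sections 7.222 and 15.23, again with one statement and a cross-reference.
- Send sites a short memo giving the reconciled instructions.

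The cost is protocol wording and the memo. No design parameter or analysis has to change.
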